TITLE:

**The Effects of Platelet-Rich Plasma vs Prolotherapy Injection on
Functional and Pain Scores in Supraspinatus Tendinopathy: A
Randomized Controlled Trial.**

DATE: 23RD AUGUST 2019

The Effects of Platelet-Rich Plasma vs Prolotherapy Injection on Functional and Pain Scores in Supraspinatus Tendinopathy: A Randomized Controlled Trial.

A) Background

Shoulder pain and dysfunction are frequently encountered in the clinical setting. It is a complex problem and affects the person's ability to carry out daily activities and work. The point prevalence of shoulder pain varies from 14% to 21% in the general population^{1,2}. A 14-years follow up study showed the prevalence of shoulder pain increased by 8.5% from the 1990s to 2004³. In primary care, the common causes of shoulder pain and disability are rotator cuff disorders, glenohumeral disorders and acromioclavicular joint disease⁴. Rotator cuff tendinopathy is defined as "pain and weakness, most commonly experienced with movements of shoulder external rotation and elevation, as a consequence of excessive load on the rotator cuff tissues"⁵. The pathology of rotator cuff tendon injury is in a continuum from underloaded/overloaded tendon to reactive tendinopathy, tendon disrepair and finally degenerated tendon⁶. Understanding of the pathological and repair process will enhance the management of a patient with such pathology.

Treatment options ranges from conservative, which consist of non-invasive such as rehabilitation to more invasive injection procedure and finally, surgical treatment. A systematic review showed limited evidence that surgery is more effective in treating rotator cuff tear than conservative treatment alone⁷. At an early stage, the use of anti-inflammatory, exercise and electrotherapeutic modalities are to control the inflammatory phase of tendon disease. However, despite the treatment above, recalcitrant tendinopathy may manifest because, once damaged, the biological and biomechanical properties of tendon tissue never completely restored. Healing times in chronic tendinopathies are prolonged as tendons are relatively less vascular and local blood flow is less than verged delivered to the muscles. Thus, in recent years, the use of platelet rich plasma and prolotherapy has been emerging as a treatment option for rotator cuff tendinopathy⁸. Platelet rich plasma with its supraphysiologic platelet concentration has the potential to release biologically active proteins that promote cellular recruitment, growth and morphogenesis. Tendon healing is thought to be stimulated via enhanced fibroblast migration and proliferation, increased the tissue vascularization and collagen deposition⁹.

Prolotherapy is an injection of small volumes of an irritant such as dextrose into the insertion sites of the damaged tendon, which promotes the growth of normal tissue. Studies hypothesize that the injected substance mimics the natural healing processes by facilitating a

local inflammatory cascade, which triggers the release of growth factors and collagen deposition¹⁰. Both interventions showed a good outcome for the treatment of rotator cuff tendinopathy.

Hypothesis:

1. Participants treated with prolotherapy injection showed a significantly higher clinical and functional scores compared to control group
2. Participants treated with platelet-rich plasma injection showed a significantly higher clinical and function scores compared to control group

Problem statements:

Platelet rich plasma and prolotherapy have been the option treatment for tendinopathy, particularly in lateral epicondylitis and Achilles tendinosis. However, the study on the rotator cuff is still limited. No study compares the effect of PRP to prolotherapy is available. Furthermore, the reviews on the factors that may influence the outcome were minimal.

Literature Review

Traditionally, the first-line management of rotator cuff tendinopathy included anti-inflammatory approach by using NSAIDs or corticosteroid. However, several studies demonstrate little or no inflammation is present in tendinopathy. Histopathologic changes associated with tendinopathy include degeneration and disorganization of collagen fibers, increased cellularity, and minimal inflammation. Macroscopic changes include tendon thickening, loss of mechanical properties, and pain. PRP and prolotherapy are believed to kick start the inflammatory process and promote tendon healing¹¹.

The study on the role of PRP for rotator cuff healing is limited. Most of the study assess the clinical effect of PRP injection after arthroscopic rotator cuff repair^{14,15}. Besides that, majority systematic reviews on the use of PRP not only limited to rotator cuff problem but included other tendinopathies including lateral epicondylitis and Achilles tendinopathies. Moreover studies, vary in PRP preparation methods and PRP class (leukocyte poor vs leukocyte rich PRP) as well as the volume of PRP injected into the tendons (ranges from 1 ml to 5 ml). Studies also differs in the use of platelet activation, and the use of lignocaine before injection^{12,16,17}. In general, the PRP was more efficient than control in reducing tendinopathy pain, with an effect size of 0.47 (95% CI 0.22 to 0.72, $p < 0.001$), signifying a moderate treatment effect⁹.

The use of prolotherapy is based on the hypothesis that hypertonic dextrose solutions in the extracellular matrix provide local tissue irritation that initiates an acute inflammatory response and improves fibroblast proliferation and subsequent collagen synthesis, which provides healing and tissue renewal¹⁸. Previous studies differes in the types of prolotherapy used for rotator cuff tendinopathy. Various substances were used by previous studies which include dextrose, phenol-glycerine-glucose (P2G), and sodium morrhuate. Results of the studies were inconsistent, ranging from no effect¹⁹ to some functional improvement²⁰ and pain reduction¹³.

A recent systematic review comparing the effectiveness of injection therapies in rotator cuff pathology concludes: “corticosteroid was more effective only in the short-term in both pain reduction and functional improvement. Network meta-analysis indicated that prolotherapy significantly reduced pain compared with placebo in the long-term [over 24 weeks, SMD: 2.63, 95% confidence interval (CI): 1.88-3.38]; meanwhile PRP significantly improved shoulder

function compared with placebo in the long-term (over 24 weeks, SMD: 0.44, 95% CI: 0.05-0.84)".²¹

B) Research Objective:

1. To investigate the effects of platelet rich plasma injection on clinical and functional outcome for the treatment of rotator cuff tendinopathy.
2. To investigate the effects of prolotherapy injection on clinical and functional outcome for the treatment of rotator cuff tendinopathy.
3. To compare the effect of platelet rich plasma vs prolotherapy injections for the treatment of rotator cuff tendinopathy
4. To analyses the factors that may result in the different outcome between PRP and prolotherapy intervention.

C) Methodology

Research Plan

This study will implement a three-armed double-blind, randomized control trial design. The study will run for 2 years. Recruitment will be for 12 months with a final follow-up at 6 months post treatment.

Recruitment centers and participant

Participants will be recruited at the University Malaya Medical Centre from Sports Medicine clinic, Orthopedic clinic, Rheumatology clinic and Primary Care clinic. Interested participants will undergo an eligibility assessment before recruitment.

Inclusion criteria are:

- 1) Individual age 18 and above
- 2) Shoulder pain more than 6 weeks3 months
- 3) Diagnosis of painful rotator cuff tendinopathy by Sports Physician/ Orthopaedic Sports Surgeon: by clinical test and ultrasound

Exclusion criteria are:

- 1) Patients with the following medical conditions: autoimmune rheumatology disease, immunocompromised, blood disorder (thrombocytopenia and anemia).
- 2) Patients with the following shoulder conditions: referred pain from cervical, recent shoulder surgery, shoulder instability and dislocation, complete rotator cuff tear, Adhesive capsulitis, grade III acromion (Biligani classification) based on the radiological finding.
- 3) Patient with the following medications: anti-coagulant treatment, steroid injection in less than 2 months
- 4) Patient with the following laboratory findings: Haemoglobin level less than 10 g/L and/or platelet count less than 100,000/ μ L
- 5) Unable to follow study protocol

Sample size calculation and estimation

The sample size was estimated based on the primary outcome of functional score. Improvement was defined by a decrease in the mean Shoulder Pain and Disability Index (SPADI) of 17.7 ± 3.7 in the platelet-rich plasma group¹¹ and 16.12 ± 12.82 ¹¹ for prolotherapy. For this study, the sample size was calculated after taking into account the desired statistical significance level set at 5%, and the power of the study set at 80%, with type I error rate of less than 0.05 is permitted and a false-negative rate of less than 0.20. The sample size is calculated using the G*Power version 3.1.9.2 software¹¹. With the assumption of 30% drop out, hence, to detect a difference in the functional outcome, a minimum of 30 patients in each group is required.

Procedures

Informed consent will be obtained from the patients before intervention. All participants are required to complete the functional questionnaire (name of the functional questionnaire = SPADI??). Participants will be assessed by Sports Physician for eligibility. Subsequently, ultrasound assessment will be performed by one musculoskeletal (MSK) radiologist or a Sports Physician with more than 10 years' experience in performing MSK ultrasound. Blood will be sent for full blood count test to assess the hemoglobin and platelet levels. A plain shoulder radiography (indicate views that will be ordered) will also be

performed to exclude Type III acromion. Electromyogram and strength testing will be done at the first visit for all patients.

Patients who fulfilled the study criteria will be randomly assigned using computer-generated block randomization to receive either PRP, prolotherapy or normal saline injections. On the procedure day, blood will be withdrawn from all the patients to ensure blinding of participants. A covered syringe contains the solutions will be prepared by the investigator to ensure its content is not visible. The procedure will be performed under ultrasound guidance with the patient sitting on a chair, in a modified crass position. All shoulder injection will be performed by a co-investigator who are not involved in outcome measure assessment of patient's progress. Post injection, the patients will be advised to rest, and avoid vigorous shoulder activities. The patients are allowed to take paracetamol if the pain is intolerable (up to 1000mg every 6 hourly. Patient are required to record the amount of paracetamol that they take.

During the follow up, the Sports Physician and or radiologist who assess the patient at baseline will repeat the assessment. The involved physician will not be informed of the intervention received by the participants. (Refer to Figure 1: Flowchart of the study).

Intervention

Platelet rich plasma: We will use a commercially available kit (YCELLBIO Kit). The autologous PRP will be prepared in accordance with the manufacturer's guideline. Fifteen (15) ml blood will be collected, according to a standard PRP kit; this volume can produce approximately 3 mL of PRP. Two milliliters of the PRP will be delivered to the injured area under ultrasound guidance.

Prolotherapy: We will dilute dextrose 50% in bacteriostatic water to get 16.5 % solution. One to two ml of the dextrose solution will be injected into the area of painful tendinosis under ultrasound guidance.

All participants will receive single injection. The injection will be under ultrasound guided intralesional.

Outcome measures

Study assessments will include the following assessment at baseline, 3 weeks, 3 months and 6 months.

- Clinical outcome: Range of movement and special test for rotator cuff
- Functional outcome: Shoulder Pain and Disability Index (SPADI) questionnaire
- Pain: Visual analogue score (VAS)
- Ultrasound assessment characteristics: tendon thickening, changes in the normal contour and echotexture lost in the fibrillar pattern, hypoechoic changes, swelling, neovascularization, and partial tear.
- Biomechanics analysis: dynamometer for strength and electromyogram of periscapular muscle

Statistical Analysis

The primary outcome of the study which consist of the mean difference in pain and shoulder function will be analyzed with independent T-test. For secondary outcome, range of movement, strength, ultrasound findings and electromyogram result independent T-test will be used for continuous data and Fisher exact test for categorical data.

D) Expected Results/Benefit

i. Novel theories/New findings/Knowledge

Platelet rich plasma and prolotherapy is a treatment of choice for recalcitrant supraspinatus tendinopathy. However, the effect may be influenced by several factors such as clinical examination at presentation and ultrasound findings.

ii. Specific or Potential Applications:

PRP and prolotherapy can result in improvement of shoulder function in patients with chronic shoulder pain. The costs are cheaper compared to surgery.

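### The plan allows for 30% dropout but states no missing-data rule for its SPADI and VAS t-tests, so response-related loss could bias the comparison in either direction without being seen

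*Combined protocol and SAP*

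**What the plan says.** - Sample size calculation and estimation: the target is reached "With the assumption of 30% drop out", and "a minimum of 30 patients in each group is required". The allowance is not split by arm, visit or reason, and it is not used again.
- Procedures: patients are randomised "to receive either PRP, prolotherapy or normal saline injections".
- Outcome measures: "Study assessments will include the following assessment at baseline, 3 weeks, 3 months and 6 months". SPADI and VAS are both on that list. The Research Plan places the "final follow-up at 6 months post treatment".
- Statistical Analysis: the primary outcome is said to "consist of the mean difference in pain and shoulder function will be analyzed with independent T-test". The rest of that section assigns t-tests or Fisher exact tests to the secondary outcomes.

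The available text gives no analysis set, imputation rule, repeated-measures model or sensitivity analysis. It does not say which visit is tested, or whether raw scores or changes are compared, although the sample size section describes improvement as a decrease in SPADI. The flowchart is not shown and could not be checked.

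**The concern.** Enlarging a trial for dropout protects power. It does not protect against bias if the patients who leave differ from those who stay. With no other rule, a t-test at a given visit takes only the patients who have a score at that visit. At 6 months, the 3-week and 3-month scores of a patient who left after 3 months would play no part, although they show how that patient was doing. If leaving is related to response, and the arms differ in how many or which patients leave, the observed difference no longer estimates the difference among all randomised patients. A benefit over saline could be understated or overstated, and the stated analysis would neither correct nor reveal it.

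**Working it through.** **1. The plan's figures.** 30 × (1 − 0.30) = 21 patients per arm with a 6-month score, if all the loss has occurred by then. (The target of 30 does not follow from the printed SPADI means and SDs; that is a separate matter and nothing here depends on it.)

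**2. Simple form of the bias.** In one arm, bias = proportion lost × (mean of those who stay − mean of those lost). If those lost from one arm improved 5 or 10 SPADI points less than those who stayed, and loss in the other arm is unrelated to response, bias = 0.30 × 5 = 1.5 or 0.30 × 10 = 3.0 points. The sign depends on which arm it is. The 5 and 10 points are assumptions. For scale, the plan's own PRP–prolotherapy difference is 17.7 − 16.12 = 1.58 points.

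**3. Equal-SD illustration.** The true difference is 0.44 SD, from the PRP function result in the Literature Review ("over 24 weeks, SMD: 0.44, 95% CI: 0.05-0.84"). Assumed: SD 1 in both arms; visit correlation 0.5 or 0.7, constant or decaying over time; loss after 3 months; logistic dropout with slope 1 or 1.5 on the 3-month score or the 3-month change, poorer values leaving more often. Large-sample simulation gives:

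| Loss, active / saline | Raw t-test | Change-score t-test | Model using all visits |
|---|---|---|---|
| 40% / 20% | 0.44 to 0.58 | 0.44 to 0.65 | about 0.44 |
| 20% / 40% | 0.30 to 0.44 | 0.24 to 0.44 | about 0.44 |
| 30% / 30%, same slope | about 0.44 | about 0.44 | about 0.44 |

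The largest raw shift is 0.58 − 0.44 = 0.14 SD. With 18 and 24 patients left, the standard error is √(1/18 + 1/24) = 0.31, so the shift is about half a standard error.

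**4. The plan's own SDs.** The cancellation in the last row needs a common SD. The sample size section prints 17.7 ± 3.7 and 16.12 ± 12.82; here ± is read as an SD. Loss is driven by the 3-month improvement, with correlation 0.5 or 0.7 and slope 1 or 1.5:
- 30% lost in each arm, same slope per SD of that arm: the true 1.58 points becomes about +0.4 to −0.5.
- One dropout rule for both arms (slope per pooled SD, √((3.7² + 12.82²)/2) = 9.435): it becomes about −0.4 to −2.1.

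The standard error with 21 per arm is √(3.7²/21 + 12.82²/21) = 2.9 points. The first case is therefore a shift of about 1.2 to 2.1 points, or 0.4 to 0.7 of a standard error.

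**5. False-positive rate.** With no true effect, equal SDs, 30 per arm, 40%/20% loss and slope 1.5 on the 3-month score, the raw t-test rejects in 5.8% to 8.0% of trials. The change-score t-test rejects in 4.6% to 5.6%.

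**6. Limit of the remedy.** If loss depends on the unseen 6-month score (40%/20%, true 0.44), the all-visit model gives 0.51 to 0.60, the change score 0.49 to 0.62 and the raw score 0.60 to 0.64. All are biased.

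**The case against.** **The completer analysis is inferred.** This stands. The plan names neither an analysis set nor a visit. The test might be run at every visit, in which case early scores of later leavers would count at those visits, and silence does not rule out imputation. The figure of 21 applies to a 6-month test. But an unqualified t-test drops patients without a score by default, and nothing in the available text says otherwise.

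**The bias is assumed.** This also stands. Rates by arm, slopes and correlations are not in the documents. The double-blind design, with blood drawn from every patient and covered syringes, makes arm-specific dropout less likely, though not impossible. A reader might infer that the t-test will favour the active injections; the documents do not support that, since they do not say who will leave.

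**Equal loss is harmless.** A reader might infer this from the 30%/30% row, or infer that one dropout rule for all arms can only shrink the difference. Neither holds in general: the plan's own SDs break both.

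**The false-positive rate is inflated.** A reader might carry the 6% to 8% over to the planned test. It belongs to the raw-score test under one assumed pattern. The change-score test stays near 5% under the same pattern, and the plan does not say which it will use.

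**The unadjusted t-test is valid after randomisation.** True with complete data. Baseline adjustment is a separate precision gain, and it may be small or nil if correlation decays over time.

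**Conclusion.** The omission is real: a 30% loss is planned for in the sample size but not in the analysis. Direction and size of any bias are unknown. Under the equal-SD assumptions the shift runs from nil to about half a standard error in either direction, modest beside the sampling error of so small a trial. With the SDs that the plan prints, its 1.58-point difference can vanish or change sign even when both arms lose 30%; that result rests on reading ± as SD and on the assumed dropout model. The documents do not support a claim that the trial's result will be wrong, or that a repeated-measures model would remove all bias. They support a cheap improvement: scores that would reduce the bias are already scheduled, and the stated analysis does not clearly use them.

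**What to change.** In Statistical Analysis, specify for SPADI and VAS:

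- Analysis by randomised arm with a mixed model for repeated measures on the 3-week, 3-month and 6-month scores. Include arm, visit, arm-by-visit, baseline score and baseline-by-visit, with an unstructured covariance and a small-sample correction. As a check, let the covariance differ by arm, given the unequal SDs in the sample size section.
- Arm contrasts at one named visit, for example 6 months.
- Dropout reported by arm and visit.
- The t-test on observed scores kept as a sensitivity analysis.
- One not-missing-at-random sensitivity analysis covering all randomised patients, with the missing scores of each arm shifted in both directions. At 30% missing, a 0.5 SD shift in one arm moves the contrast by 0.30 × 0.5 = 0.15 SD; opposite shifts in two arms move it by 0.15 + 0.15 = 0.30 SD.

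The cost is wording and slightly more analysis work; no new data and no change to procedures. The downside is reliance on missing-at-random. If loss depends on the unseen score, the model is biased too and in some settings no better than a change-score t-test, which is why the two-directional sensitivity analysis is needed. The rule should be fixed before unblinding, so that the choice among observed, imputed and modelled results is not made on the data.

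### The stated SPADI inputs do not give 30 per group at 80% power: the one contrast they define needs about 561 evaluable per group, and the saline contrasts cannot be checked

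*Combined protocol and SAP*

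**What the plan says.** Section C, under the sample size heading, bases the calculation on the functional score, SPADI. The inputs are a "decrease in the mean Shoulder Pain and Disability Index (SPADI) of 17.7 ± 3.7 in the platelet-rich plasma group" and a decrease of 16.12 ± 12.82 for prolotherapy. Significance is 5% and "the power of the study set at 80" per cent. The software is G*Power. Attrition enters through the words "With the assumption of 30% drop out". The section's conclusion reads: "hence, to detect a difference in the functional outcome, a minimum of 30 patients in each group is required".

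It does not state which two arms are compared, the effect size entered, the sidedness, the test chosen in the software, or any value for the saline arm.

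Elsewhere the document points to two different sets of contrasts:

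- **PRP versus prolotherapy.** The title is "The Effects of Platelet-Rich Plasma vs Prolotherapy Injection on Functional and Pain Scores in Supraspinatus Tendinopathy", and objective 3 in section B is "To compare the effect of platelet rich plasma vs prolotherapy injections for the treatment of rotator cuff tendinopathy".
- **Each active arm versus control.** The two hypotheses in section A are "Participants treated with prolotherapy injection showed a significantly higher clinical and functional scores compared to control group" and "Participants treated with platelet-rich plasma injection showed a significantly higher clinical and function scores compared to control group". The Procedures section shows that the control is normal saline.

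The Statistical Analysis section plans an independent t-test for pain and shoulder function.

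**The concern.** The paragraph presents 30 per group as the result of a calculation from its SPADI inputs. Those inputs are two active-arm means only 1.58 points apart, and one of the two SDs is 12.82. A difference that small relative to its spread cannot be detected with about 30 per group. If the intended contrast is instead active versus saline, half of the calculation is missing, because the saline change is not given.

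This paragraph is the only justification of the trial's size. As it stands, a reader cannot tell which comparison has 80% power. A non-significant PRP versus prolotherapy result could then be taken as evidence that the two treatments are alike, when the trial had little chance of separating them.

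**Working it through.** **Inputs from the sample size section.** PRP decrease 17.7, SD 3.7. Prolotherapy decrease 16.12, SD 12.82. Alpha 5%, power 80%, dropout 30%. Evaluable per group: 30 × 0.7 = 21. I read the ± values as SDs. If they were standard errors, the SDs and the required numbers would be larger.

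**1. Attempt to reproduce 30, PRP versus prolotherapy.**

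- Difference: 17.7 − 16.12 = 1.58 points.
- Root-mean-square SD: √((3.7² + 12.82²)/2) = 9.44.
- Standardised difference: d = 1.58/9.44 = 0.167.
- Normal approximation, n per group = 2(1.960 + 0.842)²/d² ≈ 560. The noncentral t solution is 560.7, so 561.
- Randomised, allowing for dropout: 561/0.7 = 801.4, so 802 per group.

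Other choices of SD and sidedness (noncentral t, 80% power):

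| SD | Two-sided n per group | One-sided n per group | Two-sided power at 21 | One-sided power at 21 |
|---|---|---|---|---|
| 3.7 | 88 | 69 | 27% | 39% |
| 9.44 | 561 | 442 | 8.3% | 13% |
| 12.82 | 1,035 | 815 | 6.8% | 11% |

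The most favourable cell, 69, is more than three times 21. With all 30 per group evaluable, two-sided power at SD 9.44 is still only 9.8%. A Welch simulation with the two unequal SDs gives 8.1% at 21 and 9.7% at 30, so pooling the SDs does not drive the result.

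**2. Other readings of the same inputs.**

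- Within-arm paired change needs about 3 patients (PRP) or 8 (prolotherapy).
- Prolotherapy versus a saline arm assumed not to change: d = 16.12/12.82 = 1.257. Power is 75.8% at 10 and 80.1% at 11, so 11 evaluable per group, and 11/0.7 = 15.7, so 16 randomised.

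Neither gives 30.

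**3. What 21 evaluable per group can detect (two-sided, 80% power).**

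| Alpha per test | d | Points at SD 3.7 | Points at SD 9.44 | Points at SD 12.82 |
|---|---|---|---|---|
| 5% | 0.886 | 3.3 | 8.4 | 11.4 |
| 2.5% (split over two saline tests) | 0.983 | 3.6 | 9.3 | 12.6 |

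**4. How far the saline contrasts depend on the missing value.** This is illustration only, with equal SDs in both arms. The largest saline improvement that leaves 80% power is the active-arm mean minus d × SD:

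- Prolotherapy, SD 12.82: 16.12 − 0.886 × 12.82 = 4.8 points (3.5 with alpha split).
- PRP: 17.7 − 0.886 × SD = 14.4, 9.3 or 6.3 points at SD 3.7, 9.44 or 12.82 (14.1, 8.4 or 5.1 with alpha split).

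For prolotherapy at 21 per group, power is 98% if saline does not change and 33% if saline improves by 10 points. For PRP with a 10-point saline improvement, it is over 99%, 73% or 48% at the three SDs. The saline changes of 0 and 10 points are my assumptions.

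The Literature Review quotes a standardised PRP effect on function versus placebo of 0.44 (95% CI 0.05 to 0.84). It is not cited as a sizing input. At 21 per group it gives about 29% power (5% to 76% over the interval), and 80% power would need about 83 evaluable per group.

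**5. Precision of PRP versus prolotherapy at 21 per group.** The 95% CI half-width is t(0.975, 40 df) × SD × √(2/21): 5.9 points at SD 9.44 and 8.0 at SD 12.82, against an implied difference of 1.58.

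**The case against.** The strongest reply is that 1.58 points was never the target. The section describes expected improvement in each active arm, and both hypotheses are against control. A saline improvement of about 4.8 points, set against the stated prolotherapy inputs, would give 80% power at 21 evaluable and so 30 randomised. On that view the paragraph is incomplete rather than miscalculated.

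This stands in part. For the saline contrasts the fault is a missing assumption, and no shortfall in power has been shown. The 561 applies only if the head-to-head comparison sizes the trial. But no saline value appears anywhere in the document, and the comparison in the title and objective 3 is the only one its inputs define.

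A second reply is that a generic effect size was entered in the software. A one-sided t-test at d = 0.8 needs 20.03, so 21 evaluable, and 21/0.7 = 30. A three-group ANOVA at f = 0.40 needs about 21.1 per group, or about 30 after dropout. Either could be the origin. The document states neither, neither uses the SPADI figures, and the planned test is not an ANOVA. If one of them is the source, the paragraph misdescribes its own basis.

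A third point is fair: quoting a detectable difference only at SD 12.82 would overstate the difficulty for PRP, whose stated SD is 3.7. The replacement text should show the range.

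**Conclusion.** The concern holds. No complete reading of the stated inputs gives 30 per group at 80% power. For PRP versus prolotherapy the requirement is about 561 evaluable (802 randomised) per group, ranging from 69 to 1,035 evaluable, and power at 21 evaluable is 8.3%. This rests on the ± values being SDs and on a true difference near the implied 1.58 points.

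For each active arm versus saline, the 80% claim cannot be verified. Depending on the unstated saline change and SD, 30 per group may be ample or too small. The conclusion covers the SPADI calculation only. The stated power should be corrected before it is relied on.

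**What to change.** Keep 30 per group and replace the power statement.

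1. Name the contrast that sizes the trial, with its assumed difference, SD, sidedness and alpha per test, including the assumed saline change. If a generic effect size was entered in the software, state it and justify it.
2. State what the size delivers, for example: *With 30 randomised (21 evaluable) per group, a two-sided t-test has 80% power for a standardised difference of 0.89 at 5% per comparison, or 0.98 if alpha is split over the two active-versus-saline tests. At 5% this is 3.3, 8.4 or 11.4 SPADI points for an SD of 3.7, 9.44 or 12.82.* Say which SD is believed and why the difference is plausible. At SD 12.82 it is 11.4/17.7 = 64% of the whole assumed PRP improvement and 11.4/16.12, about 70%, of that for prolotherapy.
3. State that PRP versus prolotherapy is not powered for the implied 1.58-point difference, will be reported as an estimate with a 95% CI (expected half-width about 5.9 to 8.0 points), and that non-significance will not be read as equivalence.
4. Confirm that the ± values are SDs and cite a traceable source for each. Reference number 11 is attached to both inputs and to the software, and item 11 in the list is the software paper. An entry between items 9 and 10 has no number, which may be a loss in PDF conversion.

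The cost is one rewritten paragraph and a corrected citation, with no extra patients. The power claim may become less favourable, and the sponsor must commit to a saline assumption. Only then can the adequacy of 30 per group for the written hypotheses be judged.

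### Partial tear is known before assignment but is used neither in the randomisation nor in the primary analysis, which costs some precision and credibility but causes no bias

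*Combined protocol and SAP*

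**What the plan says.** Under Procedures (section C), eligible patients are "randomly assigned using computer-generated block randomization to receive either PRP, prolotherapy or normal saline injections". No stratification factor, block size or minimisation is given.

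Exclusion criterion 2 lists "shoulder instability and dislocation, complete rotator cuff tear, Adhesive capsulitis", so a partial tear does not exclude a patient. Outcome measures lists partial tear among several ultrasound characteristics recorded at baseline and at each follow-up. Ultrasound is part of the diagnosis, and Procedures describes it before assignment, so the finding is available in time.

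Section D, item i, says that "the effect may be influenced by several factors such as clinical examination at presentation and ultrasound findings". Research objective 4 is to study factors behind a different outcome between PRP and prolotherapy.

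Statistical Analysis compares pain and shoulder function with an independent t-test and names no covariate. The sample size section gives a mean SPADI decrease of "17.7 ± 3.7 in the platelet-rich plasma group" and 16.12 ± 12.82 for prolotherapy, and asks for 30 patients per group. It adds: "With the assumption of 30% drop out".

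**The concern.** Blocking without strata evens out the number of patients per arm and nothing else. In a three-arm trial of 30 per arm, the share of partial tears can differ noticeably between arms by chance. The plan itself places ultrasound findings among the things that may matter, holds this one before assignment, and then makes no use of it.

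If partial tear is related to SPADI or VAS change, the unadjusted comparison carries variation that could have been removed. An uneven split would also invite doubt about whatever difference is reported.

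**Working it through.** **The plan's own figure.** The planned difference is 17.7 − 16.12 = 1.58 points. The mean variance is (3.7² + 12.82²)/2 = (13.69 + 164.35)/2 = 89.02, so SD = 9.44. For 80% power at two-sided 5% (sidedness is not stated), n = 2 × (1.96 + 0.842)² × 89.02 / 1.58² ≈ 560 per arm, or 560/0.7 = 800 with dropout. The stated 30 does not follow from these inputs. That is a separate and larger matter. Here, 30 per arm is taken as given, with 30 × 0.7 = 21 completers.

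**Assumptions.** The documents give neither the prevalence p of partial tear nor its effect g on SPADI change. I take p = 20% to 50% and g = 5 to 10 points. The SD of 9.44 is treated as the spread within tear groups.

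**Step 1: precision.** With n per arm:
- Unadjusted SE = √(2 × (89.02 + g² p(1−p)) / n)
- Adjusted SE = √(2 × 89.02 / n), ignoring the very small loss from estimating one more coefficient

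At n = 30 and p = 0.30, p(1−p) = 0.21:
- g = 5: √(2 × 94.27/30) = 2.51, against 2.44 adjusted
- g = 10: √(2 × 110.02/30) = 2.71, against 2.44 adjusted

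The SE falls by about 3% to 10%. In variance terms, 94.27/89.02 = 1.06 and 110.02/89.02 = 1.24, so 30 adjusted patients per arm do the work of about 32 to 37 unadjusted.

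If the plan's SD already contains the tear variation, the unadjusted SE is 2.44. The adjusted SE is then √(2 × 83.77/30) = 2.36 at g = 5 or √(2 × 68.02/30) = 2.13 at g = 10. The relative gain is similar (3% to 13%).

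**Step 2: chance imbalance.** For one pair of arms, the SD of the difference in partial-tear proportion is √(2p(1−p)/n). The shift in the contrast is the imbalance times g. The effect needed for the 95% limit to reach 1.58 is 1.58 / (1.96 × SD).

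| n per arm | p | SD | 95% limit | g needed for 1.58 |
|---|---|---|---|---|
| 30 | 0.2 | 0.103 | 0.202 | 7.8 |
| 30 | 0.3 | 0.118 | 0.232 | 6.8 |
| 30 | 0.5 | 0.129 | 0.253 | 6.2 |
| 21 | 0.2 | 0.123 | 0.242 | 6.5 |
| 21 | 0.3 | 0.141 | 0.277 | 5.7 |
| 21 | 0.5 | 0.154 | 0.302 | 5.2 |

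At 30 per arm, the exact binomial chance of a shift of at least 1.58 in this one contrast is 0.2% to 1.3% if g = 5, and about 15% to 25% if g = 10.

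**Step 3: is it bias?** I simulated two arms of 30 with no treatment difference, p = 0.30 and g = 10 or 20. The unadjusted t-test rejected in 4.9% of trials, and the mean estimated difference was within 0.04 points of zero.

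**Step 4: effect of stratifying.** In simulation with 90 patients and blocks of 6 (an assumed size), stratifying cut the 95% limit of the PRP–prolotherapy imbalance from about 20–27 to about 4–5 percentage points.

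**Step 5: objective 4.** At 30% prevalence, 21 evaluable patients per arm split into about 6 torn and 15 intact, even with perfect balance. The SE of the PRP–prolotherapy interaction is 9.44 × √(2 × (1/6 + 1/15)) ≈ 6.4 SPADI points.

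**The case against.** Unstratified blocks are a legitimate design for 90 patients at one centre. Chance imbalance is part of the random error that the t-test's standard error already covers, as step 3 confirms. This stands in full, and it is why the point concerns precision and not validity.

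The plan does not single out partial tear. It is one of several ultrasound items, and nothing in the documents ranks it above the others or above baseline SPADI. Section D and objective 4 also concern influence on the treatment effect, whereas the precision gain depends on a prognostic effect that the documents never state. Balancing the arms does not remove effect modification. These objections also stand. Partial tear is a reasonable candidate, but its importance is assumed.

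A reader might infer that chance imbalance is likely to produce a difference as large as the one planned. The documents do not support this. At a 5-point effect a shift of that size is rare. Moreover, 1.58 is a weak yardstick: it is below one standard error of its own contrast (2.44), and it says nothing about the comparisons with saline in the stated hypotheses, for which the plan gives no difference.

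What the objection does not remove is that the plan holds a baseline finding of the kind it calls influential and uses it at neither stage.

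**Conclusion.** The point holds as a modest loss of precision and credibility. At 30% prevalence and a tear effect of 5 to 10 SPADI points, both assumed, adjustment takes the SE of the PRP–prolotherapy contrast from 2.51–2.71 to 2.44. A smaller effect would make the gain negligible.

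A shift of 1.58 points at the 95% limit needs a tear effect of about 6 to 8 points at 30 per arm, or about 5 to 6.5 points among 21 completers. It should not be read as a bias, as an inflated type I error, or as a statement by the plan that partial tear changes the result.

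**What to change.** In Statistical Analysis, replace the unadjusted t-test for SPADI and VAS with a linear model (ANCOVA) that contains treatment arm and baseline partial tear (yes/no), and report the pairwise contrasts from it. Baseline SPADI or VAS can enter the same model. Because the two planning SDs differ more than threefold (12.82/3.7 = 3.5), standard errors that do not assume equal variances would be prudent. The cost is one covariate, from an ultrasound that is already done, and the factor must be named before unblinding.

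Optionally, in Procedures, form the randomisation blocks within partial-tear strata. This needs a second list and leaves at most one incomplete block per stratum, so arm sizes may differ by a few patients. Adjustment alone would be adequate.

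Stratifying would even out partial-tear numbers across arms but would not add any. Given the interaction SE of about 6.4 points, objective 4 should be described as exploratory whichever option is taken.
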